5.1 Method of Assigning Subjects to Treatment Groups

In the single-blind RI period, all subjects will receive blinded rilonacept at the same dose through Week 12; subjects will be blinded to the time of transitioning to RW. Subjects who stopped background SOC pericarditis therapy and who achieve Clinical Response on rilonacept at RI Week 12/RW baseline will be randomly assigned in a double-blind manner to continue to receive blinded rilonacept or matching placebo using a 1:1 allocation ratio. The definition of Clinical Response is provided in [Section 6.2.2](#). An interactive web response system (IWRS) will be used to administer the randomization schedule. Biostatistics will generate the randomization schedule using SAS[®] software Version 9.4 or later (SAS Institute Inc, Cary, North Carolina) for the IWRS, which will link sequential subject randomization numbers to treatment codes. The randomization schedule will be stratified by 2 factors:

- Oral CS use at baseline (RI baseline, i.e., beginning of RI period): yes or no
- Diagnosis of recurrent idiopathic pericarditis (RI baseline): yes or no

5.2 Treatments Administered

Throughout this protocol, “study drug” refers to the investigational medicinal products: rilonacept and matching placebo. Both will be administered as applicable by SC injection.

Study drug administration will be performed once a week (every 7 ± 2 days). The interval between study drug administrations must be at least 5 days.

Study drug will be dosed as follows:

Adult Subjects (≥ 18 years old):

Rilonacept: Loading dose 320 mg administered as 2 SC injections, 160 mg each (2 ml) at RI baseline, followed by once-weekly SC injections of 160 mg (2ml).

Placebo: administered as once-weekly SC injections of 2 ml each in the RW period

Upon meeting protocol criteria for bailout rilonacept ([Sections 3.1](#) and [6.2.3](#)) in the RW period, subjects will be transitioned to open-label rilonacept 320 mg administered as 2 SC injections, 160 mg each (2 ml) at the next scheduled study drug administration date, followed by once-weekly SC injections of 160 mg (2ml).

Pediatric Subjects (≥ 12 and < 18 years old):

Rilonacept: Loading dose 4.4 mg/kg administered as 2 SC injections, 2.2 mg/kg each (maximum 160 mg each) at RI baseline, followed by once-weekly SC injections of 2.2 mg/kg (maximum 160 mg). The volume of injections will be based on the subject’s weight ([Table 5–1](#)).

Placebo (in RW): once-weekly SC injections with volume based on the subject’s weight ([Table 5–1](#), maximum 2 ml).

Upon meeting protocol criteria for bailout rilonacept ([Sections 3.1](#) and [6.2.3](#)) in the RW period, subjects will be transitioned to open-label rilonacept 4.4 mg/kg administered as 1 (maximum 2 ml) or 2 SC injections at the next scheduled study drug administration date, followed by once-weekly SC injections of 2.2 mg/kg (maximum 2 ml). The volume of injections will be based on the subject’s weight ([Table 5–1](#)).

Study drug dose/volume will be calculated by the investigator or pharmacist during site clinic visits based on body weight (as specified in the [Study Schedule of Activities](#)) using a weight-based dosing chart in **kilograms** ([Table 5–1](#)).

Table 5–1: Study Drug Dose Volume (After Reconstitution) by Body Weight in Kilograms for Pediatric Subjects Aged ≥ 12 and < 18 Years

Weight Range (kg)	Loading Dose Volume (ml)	Weekly Dose Volume (ml)
23.6 to 27.2	2 x 0.7	0.7
27.3 to 30.8	2 x 0.8	0.8
30.9 to 34.4	2 x 0.9	0.9
34.5 to 38.1	2 x 1.0	1.0
38.2 to 41.7	2 x 1.1	1.1
41.8 to 45.4	2 x 1.2	1.2
45.5 to 49.0	2 x 1.3	1.3
49.1 to 52.6	2 x 1.4	1.4
52.7 to 56.3	2 x 1.5	1.5
56.4 to 59.9	2 x 1.6	1.6
60.0 to 63.5	2 x 1.7	1.7
63.6 to 67.2	2 x 1.8	1.8
67.3 to 70.8	2 x 1.9	1.9
70.9 or greater	2 x 2.0	2.0

Study Drug Self-Administration

The first study drug dose on RI baseline will be administered at the study site. During this visit, the subject will be trained on study drug preparation and injection. In case the subject is unwilling or unable to prepare and self-inject the study drug, the subject's caregiver will be trained.

The first study drug administration for adult and pediatric subjects on RI baseline will consist of 2 SC injections, constituting a loading dose. The first injection will be prepared and administered by study site staff. The second injection will be prepared and administered by the subject or the subject's caregiver after adequate training and under the supervision of study site personnel. Subsequent once-weekly study drug doses will be self-administered SC by the subject or administered to the subject by a trained caregiver as an outpatient SC administration. If the subject or subject's caregiver is unable to prepare and inject the study drug, the subject may report for once-weekly injections to a study site, or injections can be administered by the visiting registered nurse (RN).

5.3 Identity of Investigational Medicinal Product

Rilonacept (KPL-914) is the drug being evaluated in the current study. Refer to [Section 1.3](#) for a detailed description of rilonacept's mechanism of action.

Study drug (rilonacept or placebo) is supplied in a single-use, 20 ml glass vial containing a sterile, white to off-white, lyophilized powder. Each vial is to be reconstituted with 2.3 ml sterile Water for Injection (WFI). A volume up to 2 ml can be withdrawn, which is designated to deliver up to 160 mg of rilonacept or up to 2 ml placebo for SC injection only. The resulting solution is clear, colorless to pale yellow, and essentially free of particulates.

Each rilonacept vial contains 220 mg of rilonacept lyophilized powder. After reconstitution with 2.3 ml sterile WFI, the rilonacept vial contains 80 mg/ml rilonacept, 40 mM histidine, 50 mM arginine, 3.0% (w/v) polyethylene glycol 3350, 2.0% (w/v) sucrose, and 1.0% (w/v) glycine at a pH of 6.5. No preservatives are present.

Each placebo vial contains lyophilized powder. After reconstitution with 2.3 ml sterile WFI, the placebo vial contains 40 mM histidine, 50 mM arginine, 3.0% (w/v) polyethylene glycol 3350, 2.0% (w/v) sucrose, and 1.0% (w/v) glycine at a pH of 6.5. No preservatives are present.

5.4 Management of Clinical Supplies

5.4.1 Study Drug Product Packaging and Storage

Additional information regarding the preparation, dispensation, administration, and storage of rilonacept or placebo will be described in the Pharmacy Manual.

Study drug will be provided by Kiniksa Pharmaceuticals to the study sites in the lyophilized formulation in glass vials as described in [Section 5.3](#). Each single-use vial will have a clinical label adhered to the vial. One labeled vial will be placed into a carton. Each carton will have a clinical label adhered to the outside of the carton. One tamper-evident seal will be placed on the top of the carton to securely close the lid.

Study drug is to be stored and shipped refrigerated at 2°C to 8°C (36°F to 46°F) inside the original carton to protect it from light.

5.4.2 Study Drug Accountability

The sites will receive study drug for on-site administration at study site visits. Upon receipt of study drug, the investigator (or delegate) will conduct an inventory of the supplies and verify that the supplies are received intact, at the appropriate temperature, and in the correct amounts prior to completing a supplies receipt. The investigator will confirm receipt of study drug in the IWRS and retain a copy of this receipt at the study site. The inventory of supplies at each study site will be reviewed by the study monitor.

Study drug will be dispensed to the study subjects for outpatient self-administration according to the supply chain described in the Pharmacy Manual.

The investigator will maintain accurate records of receipt of all test articles, including dates of receipt. In addition, accurate records will be kept regarding when and how much study drug is dispensed and used by each subject in the study. Reasons for deviating from the expected dispensing regimen must also be recorded. At the completion of the study, to satisfy regulatory requirements regarding drug accountability, all used and unused study drug containers must be retained by the study site/clinic and subject for cataloguing and documentation of compliance. The full process for drug dispensing, documentation, and destruction will be described in the Pharmacy Manual.

A full drug accountability log will be maintained at the study site at all times.

5.4.3 Other Supplies

Rilonacept should be reconstituted with preservative-free WFI that will be provided by Kiniksa Pharmaceuticals or designee along with 27-gauge, ½-inch needles, 3-ml syringes, alcohol wipes, gauze pads, bandages, and a puncture resistant container for disposal of needles and syringes. Only the syringes and needles provided by the Sponsor or its designee should be used to prepare and inject the study drug. The Sponsor also will provide coolers and refrigerated gel packs to ensure that the subjects transport the study drug at the proper temperature. On occasion, sites may be asked to locally procure ancillary materials.

5.5 Study Drug Overdose

An overdose is any dose of study drug given to a subject or taken by a subject that exceeds the dose described in the protocol. Any overdose must be promptly reported to the [REDACTED] Pharmacovigilance (PVG) in the same way and using the same procedures as for a serious adverse event (SAE) (Section 6.4.6), regardless of whether any AEs are associated with the overdose.

If there are AEs associated with the overdose, these should be recorded on the relevant AE/SAE sections in the eCRF; however, overdoses without signs or symptoms do not need to be recorded as AEs in the eCRF.

5.5.1 Treatment of Study Drug Overdose

The maximum amount of rilonacept that can be safely administered has not been determined. Maximum once-weekly doses of rilonacept up to 320 mg have been administered SC for up to approximately 18 months in a small number of subjects with CAPS, and for up to 6 months in subjects in an unapproved indication in clinical trials without evidence of dose-limiting toxicities. In addition, rilonacept given IV at doses up to 2000 mg monthly for up to 6 months in another subject population was tolerated without dose-limiting toxicities (Rilonacept IB). In case of overdose, it is recommended that the subject be monitored for any signs or symptoms of AEs and appropriate symptomatic treatment instituted immediately (Section 13.1, ARCALYST® Prescribing Information).

5.5.2 Other Study Drug Errors

To avoid study drug errors, it is important to note the following:

- In this study, rilonacept is designated for SC injections only. It should be taken only by the subjects participating in the study and as instructed by study site personnel.
- Guidelines regarding the management of temperature excursions during storage will be detailed in the Pharmacy Manual.
- Pediatric dosing is calculated based on body weight in **kilograms**, not pounds.

Any study drug error must be promptly reported to the [REDACTED] PVG, in the same way and using the same procedures as for an SAE ([Section 6.4.6](#))

5.6 Transmission of Infectious Agents

The lyophilized study drug is to be stored refrigerated at 2°C to 8°C (36°F to 46°F) inside the original carton to protect it from light. Study drug should not be used beyond the date stamped on the label. After reconstitution, study drug may be kept at room temperature, should be protected from light, and should be used within 3 hours of reconstitution. Study drug does not contain preservatives; therefore, unused portions of study drug should be discarded.

5.7 Misuse for Illegal Purposes

Rilonacept does not have addicting potential, and the risk of misuse for illegal purposes is minimal.

5.8 Prior and Concomitant Medications

Use of all concomitant medications and any changes in concomitant medications will be recorded in the subject's eCRF. The minimum requirement is that drug name and dates of administration are to be recorded. This will include all prescription drugs, herbal products, vitamins, minerals, and over-the-counter medications.

Any concomitant medication deemed necessary for the welfare of the subject during the study may be given at the discretion of the investigator. However, it is the responsibility of the investigator to ensure that details regarding the medication are recorded in full in the eCRF. The initiation of protocol prohibited medication ([Section 5.8.6](#)) requires discontinuation of study drug.

Guidelines regarding the use of concomitant medication will be detailed in the Pharmacy Manual and are summarized in the following sections.

5.8.1 Screening

Subjects included in the study may be receiving concomitant NSAIDs and/or colchicine, and/or oral CS treatment in any combination, provided that the dosages of these medications have been stable (or not increased) for at least 3 days prior to and including RI baseline (first administration of study drug), and changes in medications made within this time period (e.g., 1-time use of NSAIDs), in the opinion of the investigator, are not anticipated to significantly alter assessments of baseline disease activity.

Analgesics can be used at the discretion of the investigator during screening activities prior to the first study drug dose, but only after the subject has documented a pericarditis pain level ≥ 4 on the 11-point NRS within 7 days prior to and including RI baseline (first administration of study drug).

Subjects can enter the study on prednisone (or equivalent dose) not exceeding 60 mg/day for adults and not exceeding 0.5 mg/kg/day (with a maximum dose of 60 mg/day) in pediatric subjects.

5.8.2 Single-blind RI Period

- 1-week Stabilization period, during which rilonacept is administered in addition to SOC pericarditis therapy and ongoing pericarditis episode is treated. All concomitant pericarditis medications including NSAIDs, analgesics, colchicine and CS will remain stable, unless the dosing must be decreased or stopped in the judgement of the investigator due to an AE.
- 9-week background medication Weaning period, during which subjects are weaned off background SOC pericarditis therapy, as applicable, while treatment with blinded rilonacept continues. The guidelines for background medication taper and discontinuation will be provided in the Pharmacy Manual.

Corticosteroids

Starting at Week 1 and through Week 10, CS will be tapered and discontinued at a rate dependent on the dose at study entry.

Analgesics

Starting at Week 1 and through Week 10, analgesics (non-opioid and opioid) will be tapered and discontinued. Opioid analgesics can continue beyond Week 10 at stable doses through the end of the RW period if it is not feasible to discontinue them without causing withdrawal symptoms.

NSAIDs and Colchicine

Starting at Week 4 and through Week 10, NSAIDs and colchicine will be tapered and discontinued.

- 2-week Monotherapy period during which rilonacept administration continues: Subjects are required to be off all background SOC pericarditis therapy, with the exception of opioid analgesics if their discontinuation is not feasible.

5.8.3 Double-blind Placebo-controlled RW Period

During the RW period, subjects should not be receiving any concomitant medications for pericarditis, with the exception of opioid analgesics in case their taper down and discontinuation was not feasible in the RI period.

5.8.3.1 Concomitant Medication Upon Pericarditis Recurrence

Subjects meeting protocol criteria for bailout rilonacept

Upon pericarditis recurrence and meeting protocol criteria for bailout rilonacept (Sections 3.1 and 6.2.3) and completing the diagnostic workup as confirmed by the [REDACTED] medical monitor, subjects will be transitioned to open-label rilonacept, as described in Section 3.1. Because open-label rilonacept can be administered only if at least 5 days have passed from the last blinded study drug administration, the investigators are allowed to use sequential ORT, i.e., analgesics, NSAIDs, and colchicine if necessary at their discretion. The use of those medications will be detailed in the Pharmacy Manual; it is briefly given as follows:

- Analgesics (including non-opioid and opioid) can be used for pain control prior to completing the diagnostic workup for a recurrent pericarditis episode. The use of analgesics during pericarditis recurrence evaluation will provide pain relief for subjects without impacting their CRP levels or other objective components of the diagnostic workup.
- After the diagnostic workup is completed based on the [REDACTED] medical monitor's assessment, NSAIDs followed by colchicine can be added to open-label rilonacept based on the subject's clinical status and at the discretion of the investigator.
- If, after transition to open-label rilonacept, the investigator decides that the subject requires CS for pericarditis therapy, the subject will be discontinued from rilonacept and followed through the EORW visit.

Subjects not meeting protocol criteria for bailout rilonacept

If, based on the investigator's judgement, the subject is experiencing pericarditis recurrence that does not meet the protocol criteria for bailout rilonacept (Sections 3.1 and 6.2.3) but does require additional treatment, the subject will continue blinded study drug, and the investigator should manage the pericarditis recurrence using sequential ORT for pericarditis, i.e., analgesics, NSAIDs, colchicine as described in the Pharmacy Manual and outlined briefly below:

- Analgesics (including non-opioid and opioid) can be used for pain control prior to completing the diagnostic workup for a recurrent pericarditis episode. The use of analgesics during pericarditis recurrence evaluation will provide pain relief for subjects without impacting their CRP levels or other objective components of the diagnostic workup.
- After the diagnostic workup is completed based on the [REDACTED] medical monitor's assessment, NSAIDs followed by colchicine can be added to blinded study drug based on the subject's clinical status and at the discretion of the investigator.
- If, after the addition of NSAIDs and colchicine, the investigator decides that the subject requires CS for pericarditis therapy, the subject will be discontinued from blinded study drug and followed through the EORW visit.

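### Section 5.8.3.1 allows new rescue analgesics before the recurrence workup is complete and does not place the workup pain score, one of the two bailout conditions, ahead of the first dose

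*Protocol*

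**What the plan says.** Section 5.8.3.1 has two branches, one for subjects who meet the bailout criteria and one for those who do not. Both carry the same statement: "Analgesics (including non-opioid and opioid) can be used for pain control prior to completing the diagnostic workup for a recurrent pericarditis episode". It is identical in protocol versions 1.0 and 1.1. The justification is that analgesics relieve pain "without impacting their CRP levels or other objective components of the diagnostic workup".

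Under Section 6.2.3, bailout needs at least one day with NRS ≥ 4 and one CRP ≥ 1 mg/dL, on the same day or no more than 7 days apart. Section 6.1.6.1 lists the NRS among the required assessments of the recurrence visit, without an order and with some assessments possibly done remotely.

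In the second branch, a subject judged to have a recurrence that does not meet the criteria is handled as follows: "but does require additional treatment, the subject will continue blinded study drug". Once the workup is complete, "NSAIDs followed by colchicine can be added to blinded study drug".

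At screening, Section 5.8.1 does fix an order. Analgesics are allowed "but only after the subject has documented a pericarditis pain level ≥ 4 on the 11-point NRS".

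**The concern.** The pain score is the one part of the bailout rule that an analgesic is meant to change, and the stated justification leaves it out. If a new analgesic is taken first and the score is recorded afterwards, the score may fall below 4 although the untreated pain was above it. The subject would then be managed in the second branch and stay on blinded drug, which may be placebo.

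Two things are at stake. One is prompt bailout: Section 3.1.6 defends the placebo arm on the ground that subjects leave blinded treatment once pain and CRP reach the stated thresholds. The other is the date of the other-secondary endpoint time to NRS ≥ 4 (7.2.2), which could be late or missed.

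**Working it through.** No protocol figure depends on this point, so the check is a reading of the rules side by side, plus one count.

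**1. What fixes the time of an NRS score in the RW period**

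| Section | Rule on timing | Relative to a rescue analgesic |
|---|---|---|
| 6.2.1.2 | Daily; same time of day recommended; before the injection on dosing days | Not mentioned |
| 6.1.6.1 | NRS required at the recurrence visit | No order given |
| 6.2.3 | Medical monitor confirms the workup is complete before the event is treated | Analgesics are let through earlier by 5.8.3.1 |
| 5.8.3.1 | Analgesics allowed before the workup is complete | No score-first condition |

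**2. Can a subject lack a pre-analgesic score for the event?** Yes. Suppose the day's diary entry is made, pain starts later that day, and an analgesic is taken before the next entry. The next diary score and the workup score are then both recorded under the analgesic, and no rule has been broken.

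**3. How much the diary protects.** Reading the 7-day rule in 6.2.3 as running in both directions, the diary days that can pair with one qualifying CRP are 7 before + 1 on the day + 7 after = 15. A score of 4 or more on any one of them meets the pain condition. Bailout on that CRP value is missed only if none of the 15 days reaches 4. That is substantial protection, but not a guarantee when effective pain relief continues.

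**4. Who is exposed.** The first branch of 5.8.3.1 is for subjects who already meet the criteria, so a qualifying score exists. The gap concerns subjects not yet shown to meet them, and so mainly the second branch.

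**5. Which analgesics matter.** Only new ones. During the RW period subjects take no pericarditis medication, "with the exception of opioid analgesics in case their taper down and discontinuation was not feasible". Stable NSAIDs, colchicine and corticosteroids are also allowed at entry (5.8.1). The threshold of 4 was therefore never free of background treatment, and the point is limited to a score lowered by a newly started rescue dose.

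**6. Can the order be reconstructed afterwards?** Not reliably. Section 5.8 asks that "details regarding the medication are recorded in full in the eCRF", but also says: "The minimum requirement is that drug name and dates of administration are to be recorded". Dates alone do not show whether a dose came before or after a score on the same day.

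**7. Which analyses are touched.** Recurrence in 6.2.3 is typical pain with supportive objective evidence, confirmed by the Clinical Endpoint Committee; it has no NRS threshold. Time to NRS ≥ 4 lies outside the gatekeeping procedure, which covers the primary and major secondary endpoints (7.7.3).

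**The case against.** The strongest case against has four parts.

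- **The diary already covers it, and the screening contrast is not a contradiction.** Daily scoring starts only at run-in baseline (6.2.1.2), so Section 5.8.1 needs a specifically documented score that later periods get from the diary. This largely stands. The screening rule shows that the protocol can set such an order; it does not show an inconsistency. What remains is step 2 above.
- **The detail may be elsewhere.** Section 5.8.3.1 describes itself as a brief outline of the Pharmacy Manual, which is not shown. Nor is the NRS wording in Appendix 13.2; an item on worst pain over a period would be less affected. Both could shrink the point. But the protocol itself states the permission and gives a reason that omits the pain score.
- **Analgesics first is the intended design.** Sequential rescue starts with analgesics, and pain held below 4 may mean that bailout severity was not reached. That is a fair reading for some subjects, but without a prior score they cannot be told apart from those whose score was masked.
- **An extra, pain-triggered score would change a fixed-time daily measure.** Section 6.1.6.1 already requires an event-triggered NRS at a suspected recurrence. The change concerns only its place in the sequence.

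A reader might infer that analgesics are permitted before any NRS is recorded. The text does not support that. It speaks of completing the workup, not of starting it, and diary scores exist throughout the RW period. A reader might also infer lost primary events or power; step 7 gives no basis for that.

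**Conclusion.** The point holds as a narrow gap in ordering. The protocol allows a new analgesic ahead of the workup NRS and justifies this only by measures that the drug does not affect. The pain score decides half of the bailout rule. The likely harm is delayed bailout for some subjects, possibly on placebo, and a late or missed date for one endpoint outside the alpha-controlled set.

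The number affected cannot be derived: the documents give no rate of masked scores, and none is assumed here. No effect on the primary test, the alpha-controlled tests or power is claimed. The conclusion assumes that the Pharmacy Manual does not already set the order and that the NRS item is sensitive to recent pain relief. The change is worth making because it is cheap, not because the trial's main result is at risk.

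**What to change.** Keep analgesics available as now. In Sections 6.1.6.1 and 5.8.3.1 (mainly the second branch), state that:

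- at a suspected recurrence, the NRS already required for the workup is recorded immediately before the first new rescue analgesic dose;
- stable opioids continued from the run-in period do not count as new;
- pain relief is not withheld if the entry is missed;
- this score counts for the bailout check (6.2.3) and for time to NRS ≥ 4 (7.2.2).

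The step can be added to the recurrence instruction already given at the RW baseline visit (6.1.2.9). If the Pharmacy Manual already sets this order, a cross-reference is enough. Recording the clock time of the first dose and sending it to the Clinical Endpoint Committee with the score would be useful but optional.

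The cost is one unscheduled NRS entry and a short subject instruction per suspected event.
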